## 1. INTRODUCTION

### 1.1. Study Summary

Inherited cardiac conditions (ICC) comprise any hereditary condition, which may affect heart muscle, vasculature, or heart electrical conductive system. ICCs represent a major cause of heart disease in all age groups, and have significant implications for patients and their families. Symptoms vary considerably, from no symptoms to sudden death. Our understanding of these conditions has increased over the past decade, however significant limitations remains in diagnosis and risk stratification of these patients and their families.

The NIH has defined a biomarker as “a characteristic that is objectively measured and evaluated as an indicator of normal biological processes, pathogenic processes, or pharmacologic responses to a therapeutic intervention”.

This study aims to investigate the utility of biomarkers in a large cohort of patients with inherited cardiac conditions with the aim of improving diagnosis and risk stratification. Biomarkers will be related to the presence and severity of cardiovascular disease and other markers of cardiac disease.

As part of this study, all patients with or with suspected ICCs attending clinics in Manchester (University Hospital of South Manchester (UHSM) and Central Manchester University Hospitals (CMFT)) will be approached over a 5 year period. The expectation is to recruit 1000 patients. Patients will undergo their clinic appointments in the usual manner. As part of the study, clinical parameters collected as part of routine care (e.g. clinical history, imaging findings, blood test results, genetic information) will be assessed in relation to each other and in relation to patient outcome over subsequent 10 year follow-up. In addition, a peripheral blood sample of up to approximately 20mL will be taken and stored to allow measurement of blood biomarkers relating to the heart, including genetic analysis, which will be related to the clinical parameters and outcome.

### 1.2. Hypothesis

We hypothesise that biomarkers will provide important diagnostic and prognostic information in patients with inherited cardiac conditions.

## 2. BACKGROUND

Inherited cardiac conditions (ICC) comprise any hereditary condition, which may affect heart muscle, vasculature, or conductive system. More than 50 ICCs have now been recognised as our diagnostic capabilities improve. However, whilst our understanding of ICCs and their molecular basis has increased, diagnosis and management of these conditions remains challenging owing to their heterogeneity, both genetically and phenotypically.

Sudden death may be the first presentation of ICC, and a new diagnosis has significant implications for patients and family members. Risk may be augmented by a multitude of clinical and genetic factors, which we do not fully understand. There is an urgent need for tools for clinicians to identify patients with ICCs, and identify those with ICCs at increased risk of adverse outcome. Biomarkers, including blood, imaging, genetic and clinical biomarkers may be help diagnosis patients with ICCs, improve prognostication/risk stratification and monitor treatment and disease progression

## 3. STUDY OBJECTIVES

To investigate the diagnostic and prognostic utility of biomarkers in a large cohort of patients with, or with suspected, ICCs.

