#### **4.2. Inclusion Criteria**

Any adult patient attending a hospital clinic that specialises in the management of patients with ICCs at UHSM or CMFT.

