#### **4.3. Exclusion Criteria**

Age < 16 years, imprisonment, inability to provide informed consent.

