### **5. STATISTICAL PLAN**

#### **5.1. Sample Size and Power Calculation**

We will ask each adult patient scheduled to attend hospital clinics that specialise in the management of patients with ICCs at UHSM and CMFT to participate in this research study. The expectation is that over a 5 year period, approximately 200 participants per year may be enrolled in this study. Due to the diversity of the variables being collected, all patients who sign consent will provide meaningful information for this study.

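### The diagnostic analysis is not confined to, or stratified by, patients whose ICC was still undecided at blood sampling, so a whole-cohort estimate would not apply to the patients who need a diagnosis

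*Combined protocol and SAP*

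**What the plan says.** Section 3 gives a single objective covering diagnosis and prognosis together: "To investigate the diagnostic and prognostic utility of biomarkers in a large cohort of patients with, or with suspected, ICCs". Section 1.1 confirms that both kinds of patient are approached: "all patients with or with suspected ICCs attending clinics in Manchester".

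Eligibility does not depend on diagnostic status. Section 4.2 admits "Any adult patient attending a hospital clinic that specialises in the management of patients with ICCs at UHSM or CMFT", and the exclusions in section 4.3 are "Age < 16 years, imprisonment, inability to provide informed consent". None concerns a previous ICC diagnosis.

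The diagnostic need is set out in section 2: "There is an urgent need for tools for clinicians to identify patients with ICCs".

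Section 5.1 names no diagnostic analysis set. It says, citing the diversity of the variables collected, that "all patients who sign consent will provide meaningful information for this study".

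Section 5.2 plans multivariable regression of biomarkers against cardiovascular disease, comparisons between patients with differing marker levels, and survival analysis. It gives no stratum by diagnostic status, no reference diagnosis and no measure of accuracy. Section 4.6.1 says that clinical data are recorded at the visit, but does not list whether ICC was established or undecided when the blood was drawn.

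**The concern.** A diagnostic tool serves people whose status is open. A clinic that manages ICC also sees people whose ICC is already known. If both groups are analysed together, the known patients enter only as cases, while every non-case comes from the suspected group. The resulting estimate mixes two questions: whether the marker recognises ICC that has already been diagnosed, and whether it helps decide the undecided. Only the second is the need described in section 2.

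The diagnostic half of the sole objective is at stake. A marker could be reported with predictive values, and possibly discrimination, that do not hold in suspected patients. Follow-up runs for 10 years, so reconstructing later who was undecided at sampling is less reliable than recording it at the time, and leaves room for choice after results are known.

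**Working it through.** **The plan's own figure.** Section 1.1 says "The expectation is to recruit 1000 patients". Section 5.1 says "over a 5 year period, approximately 200 participants per year may be enrolled in this study". 5 × 200 = 1000, so the two agree. The documents give no alpha, power, effect size, prevalence or accuracy target, so there is no power calculation to reproduce.

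**Inputs.** Only the 1000 comes from the documents. The share of established patients, the ICC prevalence among suspected patients, the marker shifts, and the sensitivity and specificity below are all assumptions.

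**Step 1: prevalence and PPV.** Assume half the cohort is established, 20% of suspected patients prove to have ICC, sensitivity is 0.70 and specificity is 0.90.

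- Of 1000 patients, 500 are established and 500 suspected. The suspected group holds 100 cases and 400 non-cases.
- Pooled prevalence = (500 + 100)/1000 = 0.60, against 0.20 among suspected patients.
- Suspected only: 0.70 × 100 = 70 true positives and 0.10 × 400 = 40 false positives. PPV = 70/110 = 0.636.
- Whole cohort: 0.70 × 600 = 420 true positives and the same 40 false positives. PPV = 420/460 = 0.913.

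The direction does not depend on marker levels. At a given cut-off, established patients add true positives and false negatives, but no false positives or true negatives. Pooled PPV is therefore too high whenever any established patient tests positive. Negative predictive value moves the other way: 360/(360 + 30) = 0.923 among suspected patients and 360/(360 + 180) = 0.667 in the whole cohort.

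With 30% to 70% established and 20% to 50% prevalence among suspected patients, pooled prevalence runs from 0.30 + 0.70 × 0.20 = 0.44 to 0.70 + 0.30 × 0.50 = 0.85.

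**Step 2: AUC.** For a normal marker with equal variances, AUC = Φ(d/√2), where d is the shift of cases from non-cases in SD. Pooled AUC = w × AUC(established) + (1 − w) × AUC(suspected cases), where w is the share of all cases already established.

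- *Established cases more marked (1.2 SD against 0.5 SD).* Φ(1.2/√2) = 0.802 and Φ(0.5/√2) = 0.638.
  - w = 0.40: 0.40 × 0.802 + 0.60 × 0.638 = 0.70
  - w = 0.70: 0.70 × 0.802 + 0.30 × 0.638 = 0.75
  - w = 0.85: 0.85 × 0.802 + 0.15 × 0.638 = 0.78
- *Smaller shifts (0.8 SD against 0.4 SD).* Pooled AUC is 0.65 to 0.70 over the same mixes, against 0.61.
- *Equal shifts (0.5 SD in both).* Pooled AUC is 0.638, with no bias.
- *Established cases less marked (0.25 SD against 0.5 SD), for example because treatment lowers the marker.* Φ(0.25/√2) = 0.5702. With 30% established and 50% prevalence among suspected patients, w = 300/(300 + 350) = 0.462 and pooled AUC is 0.462 × 0.5702 + 0.538 × 0.6382 = 0.607. With 70% established and 20% prevalence, w = 700/(700 + 60) = 0.921 and pooled AUC is 0.921 × 0.5702 + 0.079 × 0.6382 = 0.576. Both understate 0.638.

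**Step 3: is a suspected-only analysis feasible?** With 30%, 50% or 70% established, 700, 500 or 300 of 1000 remain. At 20% to 50% prevalence that gives 60 to 350 cases and 150 to 560 non-cases. The Hanley-McNeil variance is [A(1 − A) + (m − 1)(a − A²) + (n − 1)(b − A²)]/(mn), with m cases, n non-cases, A = 0.638, a = A/(2 − A) and b = 2A²/(1 + A). The 95% half-width is 0.041 for 350 cases and 350 non-cases, and 0.082 for 60 cases and 240 non-cases.

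**The case against.** The strongest reply is that section 5.2 does not describe a pooled case-versus-non-case analysis. It names no AUC, sensitivity or reference diagnosis, so spectrum bias is a risk that depends on how the gap is filled. That is correct, and the point is conditional for this reason. It does not remove the point: the objective is diagnostic, the cohort is mixed, and the only analyses specified take the cohort as a whole.

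A reader might infer that diagnostic utility would necessarily be overstated because established patients represent more developed disease. The documents do not support this. Section 1.1 describes symptoms ranging from none to sudden death, and section 2 says sudden death may be the first presentation, so severity need not follow diagnostic status. Section 2 also expects biomarkers to track treatment, which could lower levels in established patients. The direction of any AUC bias is therefore open. Only the inflation of prevalence and PPV follows whatever the marker levels.

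Two further replies have force. The statement in section 5.1 about all consenting patients concerns the whole study and is not a claim about diagnosis. Clinical history is already collected, so status could probably be recovered at analysis. Recovery would still be less secure than prospective recording, and nothing in the plan commits to it.

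Finally, restricting the population is not enough by itself. Section 2 counts imaging, genetic and clinical findings as biomarkers, and these may form part of the routine diagnosis. A marker that helps define the diagnosis cannot be fairly tested against it. The fix has to deal with this.

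**Conclusion.** The point holds in conditional form. The plan pursues a diagnostic objective in a cohort of established and suspected patients, without separating them by status at sampling. Followed as written, it cannot show whether a marker helps the undecided patients identified in section 2.

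A whole-cohort estimate would inflate prevalence and PPV, by 0.91 against 0.64 in the worked example. AUC would be too high if established cases have more marked levels, unchanged if levels are equal, and too low if treatment lowers them. Every size quoted rests on assumed case mix, prevalence, shifts, sensitivity and specificity, because the documents give none of these.

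Mixed enrolment is not itself a fault. It suits the prognostic half of the objective, and no eligibility rule needs to change.

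**What to change.** - **Section 4.6.1:** record at the clinic visit whether ICC is established or undecided at blood sampling.
- **Section 5.2:** state that the primary diagnostic analysis uses only participants undecided at sampling. Report AUC, sensitivity and specificity against ICC confirmed or excluded after routine work-up, with the marker under test not used to define that diagnosis.
- **Section 4.6.2:** hospital records are already a source, but the section speaks of cardiovascular disease status. Name confirmation or exclusion of ICC as an item to extract.
- **Reporting:** give the number whose status stays unresolved. Label any contrast of established patients with those in whom ICC was excluded as descriptive.
- **Prognostic and severity analyses:** keep the full cohort.

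The cost is one case report form item, a short paragraph in section 5.2 and one extraction item, with no extra visit or sample. The downside is a smaller diagnostic set, 300 to 700 of 1000 under the assumptions above, with AUC half-widths of about 0.04 to 0.08 before losses to unresolved status. For imaging, genetic or clinical markers that belong to the routine work-up, keeping the marker out of the reference diagnosis will take more effort than for research blood markers. The plan should say how it will be done.

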## 4. STUDY DESIGN

The Role of Biomarkers in Inherited Cardiac Conditions  
Protocol No. ICC-01  
Version 1.1: 13th October 2016

#### **4.1. Overview/Design Summary**

This is an observational study of patients attending hospital clinics that specialise in the management of patients with ICCs.

#### **4.2. Inclusion Criteria**

Any adult patient attending a hospital clinic that specialises in the management of patients with ICCs at UHSM or CMFT.

#### **4.3. Exclusion Criteria**

Age < 16 years, imprisonment, inability to provide informed consent.

#### **4.4. Recruitment**

Patients due to attend hospital clinics that specialise in the management of patients with ICCs are sent appointment information regarding their clinic appointment as part of usual clinical practice. As part of the study, we will include the study Letter of Invitation and Participant Information Sheet with the information that is sent out and any questions patients have about the study will be answered during their clinic visit. When patients attend a member of the research team will ask them if they are willing to take part, discuss any aspects of the study that they wish and answer any questions. If they are willing to take part a member of the research team will ask them to sign the consent form.

Occasionally patients will attend clinic at short notice in which case the clinical information is not sent out in advance. Given the low risk nature of this study, and the large distances that patients can potentially travel to attend these clinics (tertiary service), in this situation a member of the research team will give patients the Letter of Invitation and Participant Information Sheet while they are in the waiting area. A member of the research team will discuss any aspects of the study that they wish and answer any questions. If they feel that they have had sufficient time to understand the study and what participation involves, and are willing to take part, a member of the research team will ask them to sign the consent form.

#### **4.5. Consent**

Patients are required to read the Patient Information Sheet. Fully informed written and verbal consent will be gained from patients before they elect to participate.

#### **4.6. Details of Visits**

There will be no visits in addition to standard clinical care.

##### **4.6.1. Clinic Visit**

Patients will attend clinic, and any additional clinically indicated hospital appointments, in the usual manner. A peripheral blood sample of up to approximately 20mL will be taken for blood markers of cardiac disease and genetic analysis. Clinical data, including that relating to any imaging, blood test or functional investigations, will be recorded.

##### **4.6.2. Cardiovascular status**

Follow-up information regarding cardiovascular disease status, demographics and concurrent medical conditions and treatments will be obtained over the 10 year period following the clinic visit using the following methods:

1. GP and hospital medical records.
2. Central UK bodies, registries, audits and databases (e.g. HSCIC, ONS, NICOR, MINAP) and local health bodies e.g. clinical commissioning groups.
3. Phone call to patients

None of these follow-up procedures will occur more than once yearly.

#### **4.7. Associated Risks and Benefits**

The study is associated with negligible risk. The blood sample will be taken peripherally by an experienced member of the research team. There is a rare potential risk associated with confidentiality of medical record information, however this risk will be minimised by running the study in accordance with the Trust guidelines on Confidentiality and Security and the NHS code of practice for confidential patient information.

The use of information collected for this research study may be of future benefit to patients with cardiovascular diseases.

### **5. STATISTICAL PLAN**

#### **5.1. Sample Size and Power Calculation**

We will ask each adult patient scheduled to attend hospital clinics that specialise in the management of patients with ICCs at UHSM and CMFT to participate in this research study. The expectation is that over a 5 year period, approximately 200 participants per year may be enrolled in this study. Due to the diversity of the variables being collected, all patients who sign consent will provide meaningful information for this study.

#### **5.2. Statistical Analysis**

Multivariable regression modelling will be used to examine relationships between cardiac biomarkers and cardiovascular disease while adjusting for baseline differences of subjects. Chi square or Fisher exact tests will be used to compare categorical variables between patients with different marker levels. Independent samples t tests or Mann Whitney U tests will be used to compare continuous variables between patients with differing marker levels. Survival analysis will use logrank testing and Cox regression.

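### The only objective is diagnostic and prognostic utility, but section 5.2 commits only to association analyses and to no measure of discrimination, accuracy or added value

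*Combined protocol and SAP*

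**What the plan says.** Section 3 consists of one objective: "To investigate the diagnostic and prognostic utility of biomarkers in a large cohort of patients with, or with suspected, ICCs". Section 1.1 gives the purpose as studying biomarkers "with the aim of improving diagnosis and risk stratification", and section 2 describes the need in practical terms: "There is an urgent need for tools for clinicians to identify patients with ICCs, and identify those with ICCs at increased risk". The hypothesis in section 1.2 is: "We hypothesise that biomarkers will provide important diagnostic and prognostic information in patients with inherited cardiac conditions".

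Section 5.2 is the full analysis plan. Its first element is: "Multivariable regression modelling will be used to examine relationships between cardiac biomarkers and cardiovascular disease while adjusting for baseline differences of subjects". The rest is chi-square or Fisher tests and t or Mann-Whitney tests between patients with different marker levels, then logrank testing and Cox regression for survival. Section 1.1 describes the work in the same terms: "Biomarkers will be related to the presence and severity of cardiovascular disease and other markers of cardiac disease".

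No section mentions an ROC curve or AUC, a C-index, sensitivity, specificity, predictive values, calibration, reclassification, or a comparison of models with and without the marker. No section names a reference diagnosis or a rule for setting marker cut-offs.

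**The concern.** A marker is useful for diagnosis if it separates people with an ICC from people without one, and for prognosis if it improves on the risk estimate that routine care already gives. Regression coefficients, hazard ratios and p-values bear on these questions but do not answer them. A difference can be statistically clear and still classify patients poorly, and the same adjusted hazard ratio can mean a material or a trivial improvement, depending on how well the routine predictors already perform.

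So a team that followed section 5.2 exactly would finish with associations and no estimate that addresses the objective directly. If performance measures and cut-offs are added once the data have been seen, there is room to choose the favourable ones, and accuracy at a cut-off picked from the same data tends to be optimistic.

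**Working it through.** **1. The plan's own figure.** Section 5.1 expects about 200 participants a year for 5 years: 5 × 200 = 1000, which agrees with section 1.1. This is an accrual expectation. The documents give no alpha, power, effect size, event rate or prevalence, so there is no power statement to reproduce.

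**2. Objective against analysis.**

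| Question implied by section 3 | Nearest element of section 5.2 | What it yields |
|---|---|---|
| Does the marker identify who has an ICC? | Regression on cardiovascular disease (undefined); tests between marker-level groups | Association; no accuracy estimate |
| Does the marker rank patients by risk? | Logrank, Cox | Hazard ratio and p-value; no C-index or calibration |
| Does it add to routine predictors? | Adjustment for baseline differences | Test of independent association given covariates that are not listed; not stated to apply to the Cox model |

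The third row is a partial answer. If the covariates were the routine predictors, the adjusted model would test for added information, but it still would not say how much.

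**3. Why association is not performance (illustration; all inputs except N = 1000 are assumed).** Take a marker that is normal with SD 1 in diseased and non-diseased participants, a standardised difference d = 0.2 and two-sided alpha 0.05.
- Power = Φ(d/SE − 1.96), with SE = √(1/n₁ + 1/n₀).
- 50% diseased: SE = √(1/500 + 1/500) = 0.0632; power = Φ(3.162 − 1.960) = 88.5%.
- 30% diseased: SE = 0.0690; power 82.6%. 10% diseased: SE = 0.1054; power 47.5%.
- AUC = Φ(d/√2) = Φ(0.141) = 0.556. Sensitivity at 90% specificity = 1 − Φ(1.282 − 0.2) = 14%.

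**4. One hazard ratio, several gains (illustration; all inputs assumed).** Let log hazard = s·Z + ln(1.5)·M, where Z is the routine score and M the marker, both standard normal with correlation ρ. Solve s so that ranking on Z alone gives the stated C. The full-model C is E[1/(1 + exp(−|D|))], where D is the difference in linear predictor between two participants.

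| Routine model C | Gain, ρ = 0 | Gain, ρ = 0.5 |
|---|---|---|
| 0.60 | 0.046 | 0.037 |
| 0.70 | 0.024 | 0.018 |
| 0.80 | 0.013 | 0.010 |

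A reported hazard ratio of 1.5 therefore does not fix the gain within 0.010 to 0.046.

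**5. Cut-offs chosen from the data (illustration; all inputs assumed).** With true AUC 0.75, 30% cases and a cut-off that maximises the Youden index (sensitivity + specificity − 1), simulated apparent and true values at that cut-off are 0.384 and 0.360 at n = 1000 (excess 0.024), and 0.442 and 0.345 at n = 100 (excess 0.097). The plan does not propose such a cut-off.

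**6. Precision of an added AUC.** The Hanley-McNeil variance is [A(1−A) + (n₁−1)(Q₁−A²) + (n₀−1)(Q₂−A²)]/(n₁n₀), with Q₁ = A/(2−A) and Q₂ = 2A²/(1+A). For assumed A = 0.75, Q₁ = 0.600 and Q₂ = 0.643. With 30% cases, the 95% half-width (1.96 × SE) is 0.035 at n = 1000, 0.050 at 500, 0.079 at 200 and 0.112 at 100.

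**The case against.** The strongest reply is that plan and aim are closer than the heading suggests. The hypothesis speaks of information, section 1.1 speaks of relating biomarkers to disease and outcome, and the objective is to investigate utility, not to deliver a validated test. Regression and Cox models suit that language, and section 5.2 does promise adjustment in the regression. In addition, this is an observational cohort with recorded clinical data and 10 years of follow-up; section 5.2 rules out no metric, and a C-index or AUC could be computed later from the same models.

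Much of this stands. A reader might infer that the planned analyses say nothing about utility, or that the data would be unusable. The documents support neither reading: the adjusted models are partial evidence, and the information needed for the prognostic measures is largely collected. What may be harder to recover later is diagnostic status at sampling, although it may already be within the clinical data recorded.

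The reply does not remove the point. Leaving the measures open is what allows selective reporting, and section 5.2 neither lists the covariates nor says that the Cox model is adjusted.

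It is also fair that the undefined outcome, the missing reference diagnosis and the unlisted covariates are separate specification gaps. They would remain if an AUC were simply added, and they should not be counted as extra weight here.

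**Conclusion.** The point holds: the only stated objective concerns utility, and section 5.2 commits to no analysis that measures it. It should be fixed, but it is not a fatal flaw. The conclusion rests on the text alone and depends on none of the illustrative figures.

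Those figures invite two stronger readings that the documents do not support. A reader might take the range of C-index gains, or the 14% sensitivity, as the size of the problem in this study. They come from assumed effect sizes, prevalences and routine-model performance, and so show only that association and performance can diverge. A reader might also take the cut-off optimism as a defect of the plan. The plan refers to different marker levels without saying how they are set. Even for a Youden cut-off the excess at the planned 1000 is only 0.024, and the larger value needs a subset of 100, a size that no section gives.

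Nor do the documents show that the diagnostic question must be answered mainly in participants whose diagnosis is unresolved at sampling. Section 4.2 admits any adult attending the clinics, and the number unresolved is not stated.

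**What to change.** Amend section 5.2 as follows.

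- **Prognosis (main change).** For a pre-defined outcome, fit a Cox model with a pre-listed set of the routine predictors that section 1.1 describes as "clinical parameters collected as part of routine care (e.g. clinical history, imaging findings, blood test results, genetic information" and that section 4.6.1 says will be recorded. Then add the blood marker. Report the likelihood-ratio test, change in C-index and calibration, with bootstrap optimism correction.
- **Diagnosis.** State the reference diagnosis. Report the AUC with 95% CI against it, for blood markers that do not form part of it. Report sensitivity and specificity only at cut-offs fixed in advance, or with internal validation if derived from the data.
- **Interpretation.** Base statements about utility on these measures and keep the existing association tests as supporting analyses.
- **Optional sensitivity analyses.** Restrict the diagnostic analysis to participants unresolved at sampling, or split it by ICC group. The subset size is unknown, some participants may never reach a settled diagnosis, and precision falls quickly (half-width about 0.11 at 100 participants under the assumptions above).

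**Cost.** Recruitment and visits do not change, and the prognostic part is inexpensive. The diagnostic part is the larger task: section 2 notes "More than 50 ICCs have now been recognised as our diagnostic capabilities improve", so a reference diagnosis has to be defined across many conditions and extracted from records. The follow-up in section 4.6.2 names cardiovascular disease status, not a final ICC diagnosis.

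### Section 5.2 has no internal validation for any multi-marker model and no commitment to report every marker, so claims of diagnostic or prognostic utility could rest on figures that are too favourable

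*Combined protocol and SAP*

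**What the plan says.** Section 5.2 is the whole analysis plan. Its main model is given as "Multivariable regression modelling will be used to examine relationships between cardiac biomarkers and cardiovascular disease", adjusted for baseline differences. Two-group tests compare patients by marker level, and logrank tests and Cox regression cover time to event.

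The purpose goes beyond association. Section 3 gives the sole objective: "To investigate the diagnostic and prognostic utility of biomarkers in a large cohort of patients with, or with suspected, ICCs". Section 1.1 describes the work as done "with the aim of improving diagnosis and risk stratification".

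The candidates are broad. Section 2 refers to "Biomarkers, including blood, imaging, genetic and clinical biomarkers". Section 5.1 justifies the sample with the words "Due to the diversity of the variables being collected" and gives no effect size, power or event count.

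No section lists the markers, names a main marker or endpoint, or gives a selection rule. None mentions shrinkage, resampling, a split sample or a validation cohort. Section 8 promises to share anonymised raw data, but no validation is planned from it.

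**The concern.** Utility is a claim about patients not yet seen. When the data that draw attention to a marker also supply its reported effect, that effect is on average too far from the null. When a model is judged in the patients it was fitted to, its discrimination is flattered. Both effects grow with more candidates, fewer events and weaker true signals.

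Naming a performance measure would not cure this, because an uncorrected AUC is itself an apparent value. Nor would a multiplicity rule: it limits false positives but does not remove the inflation in estimates that pass it. At stake is whether a published risk model, or a marker put forward for stratification, would perform as reported in the next clinic population.

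**Working it through.** **1. The plan's own figure.** Section 1.1: "The expectation is to recruit 1000 patients". Section 5.1: "over a 5 year period, approximately 200 participants per year may be enrolled in this study". 200 × 5 = 1000, so the two agree. This is an accrual expectation. There is no power calculation to reproduce.

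**2. Inputs.** From the documents: n = 1000, one cohort, and outcome assessed "in relation to patient outcome over subsequent 10 year follow-up". Not in the documents: number of markers, number of events, true effects and explained variation. Everything below therefore uses assumed values, shown as a range.

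**3. A single marker noticed because it is significant.** Let b be the true log hazard ratio per SD, with standard error se = 1/√events. Among estimates significant at two-sided 0.05 in the direction of the true effect, the mean is b + se × φ(a)/(1 − Φ(a)), where a = (1.96 se − b)/se.

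- 100 events, true HR 1.10: se = 0.1, b = 0.0953, a = 1.007. Mean = 0.0953 + 0.1 × 0.2403/0.1570 = 0.248, which is HR 1.28.
- 100 events, true HR 1.50: b = 0.4055, a = −2.095. Mean = 0.4055 + 0.1 × 0.0444/0.9819 = 0.410, which is HR 1.51.

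Simulation with 2 million draws per case gives the same values:

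| True HR per SD | 50 events | 100 events | 200 events | 300 events |
|---|---|---|---|---|
| 1.10 | 1.41 | 1.28 | 1.20 | 1.17 |
| 1.20 | 1.44 | 1.31 | 1.24 | 1.22 |
| 1.30 | 1.47 | 1.36 | 1.31 | 1.30 |
| 1.50 | 1.57 | 1.51 | 1.50 | 1.50 |

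**4. A multi-marker model judged in its own data.** Logistic models were simulated in 1000 patients with 100 events and scored in the same patients and in a fresh 1000. In the first three rows, three markers carry real signal (true AUC about 0.75) and the rest are noise. Repeat runs differ by about 0.01.

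| Markers in model | Apparent AUC | New-patient AUC |
|---|---|---|
| 5, three real | 0.74 | 0.74 |
| 10, three real | 0.76 | 0.73 |
| 20, three real | 0.77 | 0.72 |
| 20, all noise | 0.63 | 0.50 |

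With 200 events, the apparent AUC of the 20-marker noise model falls to 0.60.

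**5. Cross-check by expected shrinkage.** The heuristic factor is S = 1 + p/(n ln(1 − R²app)), with adjusted Cox-Snell R² = S × R²app and n = 1000. For p = 20 and adjusted R² = 0.10: R²app = 0.10/0.84 = 0.119, ln(1 − 0.119) = −0.127, and S = 1 − 20/127 = 0.84. Over assumed R² from 0.02 to 0.15, S runs from 0.80 to 0.97 with 5 parameters, 0.67 to 0.94 with 10, and 0.51 to 0.89 with 20.

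The sample needed for S of at least 0.90 is p/(0.1 × −ln(1 − R²/0.9)). At R² = 0.10 this is 850 patients for 10 parameters and 20/(0.1 × 0.1178) = 1699 for 20. The planned 1000 therefore suits a short list and not a long one.

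**The case against.** The strongest reply is that Section 5.2 proposes to study relationships with adjustment, which is association estimation. It describes no marker search, no screening step and no significance filter, and it commits to no prediction model. The diverse variables in Section 5.1 need not all be candidate markers. If a few markers were fixed in advance and all reported, selection bias would be small. With strong markers and enough events it nearly vanishes, as the HR 1.50 row shows.

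Most of this stands. A reader might infer that the plan will trawl many markers, keep the significant ones and take their effects at face value, so that published effects would be overstated. The documents do not support that. They give no number of markers and no selection rule, and silence about validation is not a statement that apparent values will be relied on.

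The objection also limits the remedy. Penalising an adjusted association model can shrink the confounder terms along with the marker and weaken the adjustment Section 5.2 wants. Ordinary confidence intervals then no longer apply. Bootstrap optimism correction adjusts discrimination and calibration slope; it does not by itself correct individual hazard ratios.

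The reply does not remove the gap. The plan commits neither to a short fixed list nor to full reporting, and its stated aim is utility and risk stratification rather than association alone.

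**Conclusion.** The concern holds in conditional form. If markers are singled out by their results, or a multi-marker model is offered for diagnosis or risk stratification, the apparent figures could be too favourable, and nothing in the plan would detect or correct this.

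The size cannot be fixed from the documents. Under the assumptions above it runs from negligible (strong markers, about five parameters, 100 or more events) to material: a true HR of 1.10 seen as 1.28 with 100 events, or an AUC too high by about 0.05 with 20 markers of which three are real. The pure-noise case, 0.63 against 0.50, is an extreme and should not be read as the expected result. The figures assume standardised markers, se = 1/√events for the log hazard ratio, logistic models for the AUC, and selection at two-sided 0.05.

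**What to change.** Add to Section 5.2, for any multi-marker diagnostic or prognostic model:

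- The number of candidate parameters is set from the observed number of events before marker-outcome results are opened.
- The whole modelling process, including any marker selection, is repeated in at least 500 bootstrap samples.
- Optimism-corrected discrimination and calibration slope are reported and used for conclusions on utility, with apparent values alongside. The slope is applied to the risk model as a uniform shrinkage factor.

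Add, for single-marker adjusted association models, that they stay unpenalised and that every marker examined is reported whatever its result.

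This needs plan wording and some programming, with no new patients, visits or samples. The downside is that the performance figures reported will be less favourable.
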